
Study Design: This is a Phase 2, randomized, open-label, active-controlled, multicenter study to evaluate the safety and efficacy of the long-acting regimen of LEN, GS-5423, and GS-2872. The study will include approximately 75 participants with sensitivity to GS-5423 and GS-2872 by protocol-defined criteria, who meet all eligibility criteria, and who will be randomized without stratification in a 2:1 ratio to Treatment Groups 1 and 3.
 
Randomized Phase
 
Treatment Group 1
 
 Participants in Treatment Group 1 will receive the long-acting regimen consisting of LEN, GS-5423, and GS-2872. Participants will discontinue their baseline oral ART following administration of the complete study drugs on Day 1 (oral LEN, subcutaneous [SC] injectable LEN, and intravenous [IV] infusions of GS-5423 and GS-2872) and will self-administer oral LEN on Day 2. Participants will also receive study drug (SC LEN and IV infusions of GS-5423 and GS-2872) at Week 26. 
Treatment Group 3
 
 Participants in Treatment Group 3 will continue their baseline oral ART as prescribed during the randomized phase. 
Extension Phase
 
Treatment Group 1
 
 At Week 52, participants in Treatment Group 1 who receive the study drugs of LEN, GS-5423, and GS-2872, and complete the study through Week 52 with HIV-1 RNA < 50 copies/mL at the preceding Week 50 visit, will be given the option to participate in the study extension phase. In the study extension phase, participants will continue to receive their randomized study drugs every 26 weeks. Participants who elect not to participate or are not eligible to participate in the extension phase will resume their baseline oral ART (or appropriate regimen selected by the investigator). 	

Treatment Group 3

Participants in Treatment Group 3 who complete the study through Week 52 (with HIV-1 RNA < 50 copies/mL at the preceding Week 50 visit and in the absence of confirmed virologic rebound (VR) throughout the randomized phase of the study) will be given the option to participate in the extension phase and receive the study drugs of LEN, GS-5423, and GS-2872 every 26 weeks. Treatment with study drugs will begin at Week 52 and at that time the baseline oral ART regimen will be discontinued.

Number of Participants Planned: Approximately 75 total participants.

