- s Refer to Section 5.3. If coadministered, infusion of GS-5423 and GS-2872 will begin immediately following (up to 1 hour after) the last SC LEN injection. If sequentially administered, infusion of GS-2872 will begin at least 15 minutes following (up to 1 hour after) the completion of GS-5423 IV infusion. The exact date and time of study drug administration must be carefully recorded. Participants will remain in a monitored clinical setting for at least 30 minutes after completion of GS-5423 and GS-2872 infusion, if coadministered or GS-2872 infusion if sequentially administered. For the Day 1 and Week 26 visits and all subsequent dosing visits, all study drugs are to be administered on the same day.

Table 2. Study Procedures Table – Screening Through Extension Phase Week 104 (Treatment Group 3)

Study Procedure	Screening		Randomized Phase						Extension Phase				ESDD ^b	Post Study Drug Follow-up ^b	
	Visit 1	Visit 2a	Day 1	Wk 12	Wk 26	Wk 38	Wk 50	Wk 52	Wk 56	Wk 64, 90	Wk 76, 102	Wk 78, 104		PSD Day 30, 90, 180	PSD Day 270, 365
Visit Window (Days)			Within 28 Days of Screening Visit 2	± 6 Days					± 6 Days					± 6 Days	
Written informed consent	X														
Medical history	X	X													
Review concomitant medications	X	X	X	X	X	X	X	X	X	X	X	X	X	X	X
Review AEs	X	X	X	X	X	X	X	X	X	X	X	X	X	X	X
Complete physical examination		X	X										X		
Focused physical examination				X	X	X		X	X	X		X		X	
Height		X													
Weight		X	X	X	X	X		X	X	X		X	X	X	
Vital signs ^c		X	X	X	X	X		X	X	X		X	X	X	
Proviral DNA phenotype	X														
Proviral DNA genotype	X														
Chemistry ^d		X	X	X	X	X		X	X	X		X	X	X	
Hematology		X	X	X	X	X		X	X	X		X	X	X	
TSH		X	X					X					X		
CD4+ and CD8+ T-cell count		X	X	X	X	X		X		X		X	X	X ^e	
Serum pregnancy test		X													
FSH ^f		X													
Urinalysis		X	X	X	X	X		X	X	X		X	X	X	
Urine pregnancy test ^g			X		X			X	X	X		X	X	X	X
HBV & HCV serology		X													
HIV-1 RNA		X	X	X	X	X	X	X	X	X	X	X	X	X	
HIV-1 genotype/phenotype ^h				X									X		
HIV reservoir assay (PBMC) ⁱ			X		X			X				X			
CCI															
eGFR		X	X	X	X	X		X	X	X		X	X	X	
ECG ⁱ		X	X		X			X				X			

Study Procedure	Screening		Randomized Phase						Extension Phase				ESDD ^b	Post Study Drug Follow-up ^b	
	Visit 1	Visit 2a	Day 1	Wk 12	Wk 26	Wk 38	Wk 50	Wk 52	Wk 56	Wk 64, 90	Wk 76, 102	Wk 78, 104		PSD Day 30, 90, 180	PSD Day 270, 365
Visit Window (Days)			Within 28 Days of Screening Visit 2	± 6 Days					± 6 Days				± 6 Days		

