- p Participants will take 2 oral LEN tablets at Week 52 at the clinic and self-administer 2 oral LEN tablets the following day (Week 52 + 1 day) at home.
- q Refer to Section 5.3. If coadministered, infusion of GS-5423 and GS-2872 will begin immediately following (up to 1 hour after) the last SC LEN injection. If sequentially administered, infusion of GS-2872 will begin at least 15 minutes following (up to 1 hour after) the completion of GS-5423 IV infusion. The exact date and time of study drug administration must be carefully recorded. Participants will remain in a monitored clinical setting for at least 30 minutes after completion of GS-5423 and GS-2872 infusion, if coadministered or GS-2872 infusion, if sequentially administered. For the Week 52, 78, and 104 visits, all study drugs are to be administered on the same day.
- [REDACTED]

Table 3. Study Procedures Table – Extension Phase Post Week 104 Through End of Study (Treatment Groups 1 and 3)

Study Procedure	Extension Phase			ESDD ^a	Post Study Drug Follow-up ^a	
	Wk 116, 142	Wk 168, 194, 220, 246, 272, 298, 324, 350, 376	Wk 130, 156, 182, 208, 234, 260, 286, 312, 338, 364, 390		PSD Day 30, 90, 180	PSD Day 270, 365
Visit Window (Days)	± 6 Days					
Review concomitant medications	X	X	X	X	X	X
Review AEs	X	X	X	X	X	X
Complete physical examination				X		
Focused physical examination	X	X	X		X	
Weight	X	X	X	X	X	
Vital signs ^b	X	X	X	X	X	
Chemistry ^c	X	X	X	X	X	
Hematology	X	X	X	X	X	
TSH				X		
CD4+ and CD8+ T-cell count	X	X	X	X	X ^d	
Urinalysis	X	X	X	X	X	
Urine pregnancy test ^e	X	X	X	X	X	X
HIV-1 RNA	X	X	X	X	X	
HIV-1 genotype/phenotype ^f	X					
HIV reservoir assay (PBMC) ^g			X			
CCI						
eGFR	X	X	X	X	X	
Plasma storage samples for virology testing	X	X	X	X		
Immunogenicity (ADA) serum sample ⁱ	X		X	X	X	X
Serum PK samples (GS-5423 & GS-2872) ^{j, k}	X		X	X	X	X
Plasma PK sample for LEN ^{j, l}	X		X	X	X	X
LEN SC administration			X			
GS-5423 IV infusion administration ^m			X			
GS-2872 IV infusion administration ^m			X			

Study Procedure	Extension Phase			ESDD ^a	Post Study Drug Follow-up ^a	
	Wk 116, 142	Wk 168, 194, 220, 246, 272, 298, 324, 350, 376	Wk 130, 156, 182, 208, 234, 260, 286, 312, 338, 364, 390		PSD Day 30, 90, 180	PSD Day 270, 365
Visit Window (Days)	± 6 Days					

CCI

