3.1.2. Extension Phase

Treatment Group 1

At Week 52, participants in Treatment Group 1 who receive the study drug of LEN, GS-5423, GS-2872, and complete the study through Week 52 with HIV-1 RNA < 50 copies/mL at the preceding Week 50 visit, will be given the option to participate in the study extension phase. In the study extension phase, participants will continue to receive their randomized study drugs every 26 weeks.

Participants who elect not to participate or are not eligible to participate in the extension phase will resume their baseline oral ART (or appropriate regimen selected by the investigator).

Treatment Group 3

Participants in Treatment Group 3 who complete the study through Week 52 with HIV-1 RNA < 50 copies/mL at the preceding Week 50 visit and in the absence of confirmed VR (as defined in Section 6.3.9.2.2) throughout the randomized phase of the study will be given the option to participate in the extension phase and receive the study drugs of LEN, GS-5423, and GS-2872 every 26 weeks at the dose specified for Treatment Group 1. Treatment with LEN, GS-5423, and GS-2872 will start at Week 52 and at that time the baseline oral ART will be discontinued.

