4.3. Exclusion Criteria

Participants who meet any of the following exclusion criteria are not eligible to be enrolled in this study:

- 1) Any prior receipt of LEN or a bNAb for HIV-1 treatment.
- 2) Receipt of long-acting injectable ARV within 6 months of Screening Visit 2.

- 3) Have been treated with immunosuppressant therapies or chemotherapeutic agents (eg, corticosteroids, immunoglobulins, and other immune- or cytokine-based therapies) within 4 weeks of Screening Visit 2 (with the exception of a single short course of corticosteroids lasting ≤ 7 days) or have a comorbid condition with an anticipated need ongoing immunosuppressive treatment during the study.
- 4) Pregnant participants assigned female at birth or plans to become pregnant during the course of the study.
- 5) Lactating participants assigned female at birth.
- 6) Participation in any other clinical study, including observational studies, without prior approval from the sponsor.
- 7) Clinically significant abnormal electrocardiogram (ECG) at the Screening Visit 2.
- 8) Hepatitis C virus (HCV) antibody positive and HCV RNA detectable.
- 9) Chronic hepatitis B virus (HBV) infection, as determined by either: positive HBV surface antigen and negative HBV surface antibody, regardless of HBV core antibody status, at the screening visit, or positive HBV core antibody, negative HBV surface antibody regardless of HBV surface antigen status, at Screening Visit 2.
- 10) Active, serious infections (other than HIV-1 infection) requiring systemic antibiotic or antifungal therapy within 30 days prior to Screening Visit 2.
- 11) Have poor venous access that would limit phlebotomy or IV infusion of study drugs.
- 12) Have a history of any of the following:
 - A) Opportunistic infection or illness indicative of Stage 3 HIV disease.
 - B) Known hypersensitivity to the study drug, the metabolites, or formulation excipient.
 - C) Malignancy within the past 5 years (prior to screening) or ongoing malignancy, other than basal cell carcinoma, or resected, noninvasive cutaneous squamous carcinoma.
 - D) Substance abuse or a psychiatric or medical condition that could, in the opinion of the investigator, compromise the participant's ability to participate in the study.

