5. STUDY INTERVENTIONS AND CONCOMITANT MEDICATIONS

5.1. Randomization

5.1.1. Randomization

Participants will be assigned a screening number in the IRT system at the time of consent.

Randomization and Day 1 visits must not occur until participant eligibility has been confirmed. Once eligibility has been confirmed, the investigator or designee will randomize the participant using the IRT system. Once a participant number has been assigned to a participant, it will not be reassigned to any other participants. The participant number assignment and randomization may be performed up to 3 days prior to Day 1 visit provided all screening procedures have been completed and participant eligibility criteria has been confirmed.

Participants who meet eligibility criteria will be randomized in a 2:1 ratio to Treatment Groups 1 and 3.

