Study Day	Treatment Group 1
Day 1	LEN 600 mg (two 300-mg tablets, PO) LEN 927 mg (two 1.5-mL injections, SC) GS-5423-2550 mg (IV infusion) GS-2872-2550 mg (IV infusion)
Day 2	LEN 600 mg (two 300-mg tablets, PO)
Weeks 26 and 52	LEN 927 mg (two 1.5-mL injections, SC) GS-5423-2550 mg (IV infusion) GS-2872-2550 mg (IV infusion)
Every 26 weeks during the extension phase	LEN 927 mg (two 1.5-mL injections, SC) GS-5423-2550 mg CCI [REDACTED] GS-2872-2550 mg CCI [REDACTED]

IV = intravenous; LEN = lenacapavir; PO = orally; SC = subcutaneous

Treatment Group 3

Day 1 Through Week 52:

Participants in Treatment Group 3 will stay on their baseline oral ART through Week 52.

Week 52:

Participants in Treatment Group 3 who are eligible and elect to participate in the extension phase will receive the study drugs of LEN, GS-5423, and GS-2872 as described below and in [Table 5](#).

Participants will receive the following study drugs. All study drugs should be administered on the same day (ie, no visit window is permitted for Week 52 study drug administration):

- Oral LEN 600 mg will be administered orally with approximately 240 mL water, without regard to food.
- SC LEN 927 mg will be administered within 30 minutes after oral LEN for loading, as 2 SC injections at separate injection sites in the abdomen, within 15 minutes.
- Infusions of GS-5423 and GS-2872 will either be coadministered (preferred option) or administered sequentially (at investigator discretion) following SC LEN injection:

— Coadministration

- GS-5423 2550 mg and GS-2872 2550 mg CCI

Infusions of GS-5423 and GS-2872 will be administered over 60 minutes.

— Sequential administration

- GS-5423 2550 mg CCI

Infusions of GS-5423 will be administered over 30 minutes.

- GS-2872 2550 mg CCI

Infusions of GS-2872 will be administered over 30 minutes.

Participants will discontinue their baseline oral ART following administration of the complete study drugs on Week 52.

Week 52 + 1 Day:

Participants will self-administer oral LEN 600 mg at home with approximately 240 mL water, without regard to food, at approximately the same time as the oral LEN dose on Week 52.

Every 26 Weeks During the Extension Phase:

At each dosing visit during the extension phase, the following study drugs will be administered:

- LEN 927 mg, as 2 SC injections at separate injection sites in the abdomen, within 15 minutes

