6.2. Screening, Participant Enrollment, and Treatment Assignment

Due to the extended laboratory processing time of the GS-5423 and GS-2872 proviral DNA phenotype testing (up to approximately 10 weeks), the screening visit will be performed in 2 parts ([Table 1](#) and [Table 2](#)). Participants meeting all of the inclusion criteria and none of the exclusion criteria will return to the clinic within 28 days after the Screening Visit 2 for the Day 1 visit. It is the responsibility of the investigator to ensure that participants are eligible to participate in the study prior to enrollment and continue to remain eligible throughout the study. The medical monitor may be contacted regarding any questions related to eligibility.

If the screening window is exceeded in an otherwise eligible participant, the participant is allowed to rescreen (Screening Visit 2) 1 time after approval from the sponsor. Once a participant has started the rescreening process, a new screening window (28 days) will begin, during which time screening procedures will be repeated.

Entry into screening does not guarantee enrollment into the study. In order to manage the total study enrollment, Gilead, at its sole discretion, may suspend screening and/or enrollment at any site or study wide at any time.

Participants must continue to take their baseline oral ART until completion of study drug administration at the Day 1 visit (Treatment Group 1) or Week 52 visit (Treatment Group 3). Once the ICF has been obtained, all screening and eligibility tests and assessments have been assessed, and study eligibility has been confirmed, participants will be randomized to receive study drug on Day 1. Participants will receive the study drugs as described in Section 5.3.

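### Optional safety improvement: Group 3 stops oral ART at Week 52 on a hepatitis B result about a year old, with no repeat serology scheduled

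*Protocol*

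**What the plan says.** Group 3 keeps its baseline oral ART for 52 weeks. Those who enter the extension then switch: "Treatment with study drugs will begin at Week 52 and at that time the baseline oral ART regimen will be discontinued" (Protocol Synopsis, Study Design). The conditions are completion through Week 52, a Week 50 HIV-1 RNA below 50 copies/mL and, in the words of Section 3.1.2, "in the absence of confirmed VR (as defined in Section 6.3.9.2.2) throughout the randomized phase of the study". Section 5.3 says that Group 3 participants "who are eligible and elect to participate in the extension phase will receive the study drugs" at Week 52. None of these names HBV.

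Exclusion criterion 9 (Section 4.3) is "Chronic hepatitis B virus (HBV) infection, as determined by either: positive HBV surface antigen and negative HBV surface antibody", or alternatively a positive core antibody with a negative surface antibody. Table 2 has a row "HBV & HCV serology" with a single mark, under Screening Visit 2. SAP Table 13-2 is the same. Table 3, which covers visits after Week 104, shows no HBV row. For Group 1, SAP Table 13-1 also has one mark, at Screening Visit 2.

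Two rules govern how old a screening result may be on Day 1. Section 5.1.1 says: "Randomization and Day 1 visits must not occur until participant eligibility has been confirmed". Section 6.2 puts Day 1 within 28 days of Screening Visit 2. If that window is missed, Visit 2 may be repeated once, with a new 28-day window and the screening procedures redone. Section 6.2 also makes the investigator responsible for ensuring that participants are "eligible to participate in the study prior to enrollment and continue to remain eligible throughout the study".

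**The concern.** Week 52 is Group 3's counterpart of Group 1's Day 1: the oral LEN load is given, the long-acting regimen starts and oral ART stops. Viral suppression is rechecked two weeks earlier, and a urine pregnancy test is done before dosing where relevant. HBV status is not looked at again.

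A participant who came to meet criterion 9 after Screening Visit 2, without anyone knowing, would be taken off oral ART by a site that followed the plan exactly. Table 6 then prohibits any ARV outside the study regimen.

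The protocol gives no reason for criterion 9. The nearest indication is in Section 1.2.4: in the predecessor study's pilot cohort, a participant with chronic HBV restarted ART on Day 30. What is at stake is the safety of individual participants. No endpoint, interval or error rate depends on it.

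**Working it through.** The plan states no age for the HBV result, so there is no figure to reproduce. The inputs are:

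- Screening Visit 2 to Day 1: 0 to 28 days (Section 6.2).
- Day 1 to the switch: 52 weeks, with a window of ±6 days (Table 2).
- Group 3 size: 25 of about 75 (Section 8.11; 2:1 randomization).

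**Age of the HBV result when oral ART stops**

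- Group 1, Day 1: 0 to 28 days.
- Group 3, Week 52, nominal: 52 × 7 = 364, so 0 + 364 = 364 to 28 + 364 = 392 days.
- Group 3, window extremes: 0 + 364 − 6 = 358 to 28 + 364 + 6 = 398 days. The 358 is theoretical, because Visit 2 results must be back before randomization.

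For any given participant the Week 52 result is therefore a year older than it was on Day 1. The shortest nominal age in Group 3 is 364 / 28 = 13 times the longest allowed in Group 1.

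**Age in the extension, both groups (nominal visits, adding 0 to 28 days)**

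| Dosing visit | Days from Day 1 | Age of HBV result |
|---|---|---|
| Week 78 | 78 × 7 = 546 | 546–574 days |
| Week 104 | 104 × 7 = 728 | 728–756 days |
| Week 130 | 130 × 7 = 910 | 910–938 days |

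**Age if serology were added at Week 50**

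Nominal: (52 − 50) × 7 = 14 days at the switch. With both visits at opposite ends of their ±6-day windows: 14 − 12 = 2 to 14 + 12 = 26 days. This stays inside the 28 days that applies to Group 1.

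**Which existing checks would detect HBV**

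Liver chemistry (ALT, AST, bilirubin; Table 7) is drawn in Group 3 at Weeks 12, 26, 38, 52 and 56. It may prompt a question but cannot show the serological patterns that define criterion 9. The duty in Section 6.2 and the word eligible in Section 5.3 cover a participant already known to have HBV; no scheduled test supports them.

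**How many are affected**

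At most about 75 × 1/3 = 25 participants make this switch. The documents give no rate of new HBV infection, no vaccination status and no HBV activity of the baseline regimens, so no expected count can be computed.

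**The case against.** The case on the other side is substantial.

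- **No rule is broken.** Criterion 9 is an entry criterion and was applied at entry. A reader might infer that the 28-day limit also governs Week 52. It does not: Section 6.2 ties it to Day 1, and the protocol sets no age limit for an HBV result at the switch. The comparison with Group 1 shows an uneven standard, not a violation.
- **Known HBV is covered.** A reader might infer that the plan would switch someone known to have HBV. Sections 6.2 and 5.3 do not support that. The gap is limited to HBV that no one has tested for.
- **The predecessor case is weak support.** It might be read as HBV acquired on study, or as harm from stopping ART. Section 1.2.4 records a protocol violation, does not call it a new infection, does not say when it was found and reports no resulting injury. It shows only that ART was restarted when chronic HBV was identified.
- **HCV is also tested once.** That is true, and criterion 9 carries no stated rationale. Treating HBV differently rests on the predecessor study's own response to it, which is a modest basis.
- **The timing is late.** Section 1.4.1.2 already reports Week 52 results, and Section 8.2.1.1 places that analysis after all participants have completed Week 52 or stopped study drug. Few or no switches remain, so a pre-switch test is largely moot in this trial. This stands.
- **Group 1 is in the same position in the extension.** Its serology is just as old at Weeks 78, 104 and 130. This also stands: a post-switch test confined to Group 3 would need a stated reason.

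What survives is that oral ART is withdrawn on a year-old result, and that neither liver chemistry nor the general eligibility duty would find HBV that arose in that year.

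**Conclusion.** The point holds as an optional, low-cost safety improvement. The schedule facts are firm: one HBV serology at Screening Visit 2, no HBV condition among the switch criteria, and a result about 12 to 13 months old at the switch, against at most 28 days in Group 1. The importance is not established, and the number affected may be zero. The day counts assume visits on schedule or within the stated windows, and the group size assumes planned enrollment. Some rows of Tables 2 and 3 are blacked out, but the HBV row in Table 2 is visible and has only the screening mark. Sample size, endpoints and analyses are unaffected.

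**What to change.** 1. **Group 3 participants not yet switched (few or none).** Add HBV serology to the existing Week 50 draw, and add absence of chronic HBV as defined in criterion 9 to the conditions in Section 3.1.2 and the synopsis.
2. **Group 3 participants already switched.** Add one HBV serology to the next scheduled blood draw. Tables 2 and 3 draw HIV-1 RNA at every extension visit, so any will serve. A visit between doses (for example Weeks 64, 76, 90 or 102 in Table 2; Weeks 116, 142 or 168 onward in Table 3) is better, because the result is then back before the next dose.
3. **Action on the result.** One that meets criterion 9 goes to the medical monitor, who decides on further dosing and on return to an appropriate oral ART regimen.
4. **Group 1.** Apply the same single test in the extension, or state why it is limited to Group 3.

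The cost is one assay on an existing draw in about 25 participants, or up to about 75 with Group 1. It also needs edits to Section 3.1.2, the synopsis and the procedures tables, made through a protocol amendment with IRB approval (Sections 9.1.3 and 9.2.1) across about 55 planned centers. No extra visit is needed.

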Plasma storage samples for virology testing			X	X	X	X	X	X	X	X	X	X	X		
Immunogenicity (ADA) serum sample ^k								X		X		X	X	X	X
Serum PK samples (GS-5423 & GS-2872) ^{l, m}								X	X	X		X	X	X	X
Plasma PK sample for LEN ^{l, n}								X	X	X		X	X	X	X
Randomization			X												
HIV Treatment Preference Questionnaire			X		X			X				X			
HIVDQoL			X		X			X				X			
HIVTSQs ^o			X		X			X	X			X			
HIVTSQc ^o												X			
Continue baseline oral ART			X												
LEN oral administration ^p								X							
LEN SC administration								X				X			
GS-5423 IV infusion administration ^q								X				X			
GS-2872 IV infusion administration ^q								X				X			

CCI

ADA = antidrug antibody; AE = adverse event; ART = antiretroviral therapy; ARV = antiretroviral; CD4 = clusters of differentiation 4; CD8 = clusters of differentiation 8; DNA = deoxyribonucleic acid; ECG = electrocardiogram; eGFR = estimated glomerular filtration rate; ESDD = early study drug discontinuation; FSH = follicle-stimulating hormone; HBV = hepatitis B virus; HCV = hepatitis C virus; HIV = human immunodeficiency virus; HIV-1 = human immunodeficiency virus type 1; HIVDQoL = HIV-dependent quality of life; HIVTSQc = HIV Treatment Satisfaction Questionnaire change version; HIVTSQs = HIV Treatment Satisfaction Questionnaire status version; IV = intravenous; LEN = lenacapavir; PBMC = peripheral blood mononuclear cell; PK = pharmacokinetic(s); PSD = post study drug; RNA = ribonucleic acid; SC = subcutaneous; TSH = thyroid-stimulating hormone; Wk = week

- a Screening Visit 2 will be performed once results of GS-5423 and GS-2872 sensitivity testing from Visit 1 are reviewed and participant is deemed eligible to proceed.
- b For participants who discontinue the study prior to Week 52, only a ESDD and 30-day follow-up visit is required. For participants who receive study drug in extension phase, refer to Section 6.3.11 for ESDD and post-ESDD 30-, 90-, 180-, 270-, and 365-day follow-up visits. Counsel participant regarding the importance of continuing a complete ARV therapy in accordance with standard of care, and refer participant to an appropriate HIV treatment facility.
- c Vital signs: blood pressure, pulse, and temperature. On dosing days for LEN + GS-5423 + GS-2872, vital signs should be recorded prior to start of study drug administration and 30 minutes (± 10 minutes) after completion of both GS-5423 and GS-2872 infusion, if coadministered or the GS-2872 infusion, if sequentially administered.

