8.6. Safety Analysis

Safety data will be summarized by treatment group using the Safety Analysis Set. For Treatment Group 1, all safety data collected on or after the first dose date of study drug will be included. For Treatment Group 3, all safety data collected on or after the first dose date of study drug and up to 30 days after the last dose date will be included. All data will be summarized by treatment according to the study drug received. All collected data will be included in data listings for all enrolled participants.

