8.6.2. Adverse Events

Clinical and laboratory AEs will be coded using the current version of the Medical Dictionary for Regulatory Activities (MedDRA). System organ class (SOC), high-level group term, high-level term (HLT), preferred term (PT), and lower-level term will be attached to the clinical database.

Events will be summarized on the basis of the date of onset for the event. For Treatment Group 1, a TEAE will be defined as any AE that begins on or after the date of first dose of study drug. For Treatment Group 3, a TEAE will be defined as any AE that begins on or after the date of first dose of study drug and up to 30 days after the last dose date; or any AE leading to study drug discontinuation.

Summaries (number and proportion of participants) of treatment-emergent AEs and SAEs (by SOC, HLT [if applicable], and PT) by treatment group will be provided. Additional summaries will include summaries for AEs by grade, investigator's assessment of relationship to study drug, and effect on study drug dosing.

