8.6.3. Laboratory Evaluations

Selected laboratory data (using conventional units) will be summarized using only observed data. Absolute values and change from baseline at all scheduled visits will be summarized by treatment group.

Graded laboratory abnormalities will be defined using the grading scheme in The DAIDS Toxicity Grading Scale, Version 2.1, dated July 2017 (Appendix 11.4).

The number and proportion of participants experiencing treatment-emergent laboratory abnormalities will be summarized by treatment group. For Treatment Group 1, treatment-emergent laboratory abnormalities are defined as values that increase at least 1 toxicity grade from baseline at any time postbaseline. For Treatment Group 3, treatment-emergent laboratory abnormalities are defined as values that increase at least 1 toxicity grade from baseline at any time postbaseline up to and including the date of last dose of study drug plus 30 days. If baseline data are missing, then any graded abnormality (ie, at least a Grade 1) will be considered treatment emergent.

All laboratory abnormalities will be included in a data listing.

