7.1.5. Treatment-Emergent Adverse Events

7.1.5.1. Definition of Treatment-Emergent Adverse Events

Treatment-emergent AEs (TEAEs) in the randomized phase are defined as 1 or both of the following:

- Any AEs leading to premature discontinuation of study drug during randomized phase, or
- Any AEs that start during the TE period (Section 7)

Treatment-emergent AEs (TEAEs) in extension phase are defined as 1 or both of the following:

- Any AEs leading to premature discontinuation of study drug during extension phase, or
- Any AEs that start on or after study day 1 (extension phase) (section 3.8.1)

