7.7. Changes from Protocol-Specified Safety Analyses

No change from protocol-specified safety analyses is planned.

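### The protocol's 30-day safety cut for Group 3 is not limited to oral ART, so as written it also governs crossover participants on the 26-week regimen; it contradicts the SAP for AEs and is the only rule for extension labs

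*Protocol*

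**What the plan says.** **Protocol.** Section 8.6 includes all Group 1 safety data from the first dose onward. It then sets a different rule for Group 3, with an end point: "and up to 30 days after the last dose date will be included". Section 8.6.2 places the onset of a Group 3 TEAE "on or after the date of first dose of study drug and up to 30 days after the last dose date"; AEs that lead to discontinuation count as well. Section 8.6.3 counts Group 3 lab abnormalities "at any time postbaseline up to and including the date of last dose of study drug plus 30 days"; for Group 1 it counts them at any time after baseline.

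Section 1.2 defines study drug to include both the long-acting agents and baseline oral ART. Section 3.1.2 gives eligible Group 3 participants the Group 1 regimen every 26 weeks from Week 52. Section 6.3.11.2 follows those who stop in the extension until at least 365 days after the last dosing visit. Table 2, footnote b, sets the schedule of visits after stopping: "For participants who receive study drug in extension phase, refer to Section 6.3.11 for ESDD and post-ESDD 30-, 90-, 180-, 270-, and 365-day". Table 2 schedules AE review at every one of those visits, and chemistry and hematology up to post-study-drug Day 180.

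**SAP.** Section 7 applies the 30-day cut only to Group 3 participants who do not enter the extension. Section 7.1.5.1 counts as extension-phase TEAEs those leading to discontinuation and "Any AEs that start on or after study day 1 (extension phase) (section 3.8.1", with no end date. Section 7.2.2.1 defines treatment-emergent lab abnormalities for the randomized phase only. Section 7.7 states: "No change from protocol-specified safety analyses is planned".

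**The concern.** A 30-day tail is reasonable for a daily oral regimen. It does not suit agents dosed every 26 weeks, and the documents themselves indicate this:

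- Protocol 1.4.1.1 expects antibody concentrations above 10 µg/mL in nearly 100% of participants 6 months after a dose.
- SAP 3.8.1 defines a separate last exposure date because exposure to these drugs outlasts dosing.
- SAP 7 gives a Group 1 participant who took only oral LEN 60 days. A crossover participant given the full injected and infused regimen gets 30 days under the protocol.

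Nothing in Protocol 8.6 to 8.6.3 ends the 30-day rule at crossover. The same event, at the same time after the same long-acting dose, would be treatment-emergent in a Group 1 participant and not in a crossover participant. The analyses at stake are Week 104 and the final analysis, where extension safety is reported. The current SAP covers only the Week 52 interim, is based on Amendment 3, and summarizes only randomized-phase data by group.

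**Working it through.** **The plan's own safety figure.** Protocol 8.11 gives the chance of seeing at least one AE of 5% incidence. 1 − 0.95^50 = 92.3% and 1 − 0.95^25 = 72.3%, so both reproduce. They are not in dispute.

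**Days covered.** Inputs: cut at 30 days (Protocol 8.6); dosing interval 26 weeks = 182 days (3.1.2); follow-up of at least 365 days from the last dosing visit (6.3.11.2).

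| Period after the last long-acting dose | Days inside | Days outside | Share outside |
|---|---|---|---|
| Required follow-up, 365 days | 30 | 365 − 30 = 335 | 335/365 = 92% |
| Last dosing interval, 182 days | 30 | 182 − 30 = 152 | 152/182 = 84% |

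Time before the last dose is unaffected. A participant who stops after two doses has 182 + 30 = 212 of 364 days covered (58%).

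**Days are not events.** The documents do not say when events occur. Assume an event rate that halves every *h* days after the last dose, followed for 365 days. The share lost is 1 − (1 − 0.5^(30/h)) / (1 − 0.5^(365/h)).

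| Assumed halving time (days) | 7 | 14 | 30 | 60 | 90 | 180 | constant rate |
|---|---|---|---|---|---|---|---|
| Share of events outside the window | 5% | 23% | 50% | 70% | 78% | 86% | 92% |

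More than half are lost only if the rate halves more slowly than about every 30 days.

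**Illustration, on assumptions.** Suppose all 25 Group 3 participants cross over and an AE of 5% incidence is spread evenly over the 365 days. The chance of counting at least one is 1 − (1 − 0.05 × 30/365)^25 = 9.8% with the cut, against 72.3% without it.

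**The other reading of last dose.** If it meant the last oral ART dose, the window would close about 30 days after Week 52, which covers even less of the long-acting period.

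**Which rule applies in the extension.**

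| | Protocol, Group 3 | SAP, extension phase |
|---|---|---|
| AEs | last dose + 30 days, or leading to discontinuation | no upper limit |
| Labs | last dose + 30 days | none given |

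**Lab baseline.** SAP 3.8.1 takes the Group 3 baseline on or before randomized Study Day 1. That is about 52 × 7 = 364 days before a crossover participant's first long-acting dose.

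**The case against.** **The SAP already handles AEs.** Protocol Section 8 leaves detail and deviations to the SAP, and SAP 7 and 7.1.5.1 set no upper limit for extension AEs. This stands: extension AEs are lost only if the protocol text governs. What remains is an undeclared contradiction, since SAP 7.7 reports no change.

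**The later plan is not among the documents.** Extension labs are outside the Week 52 SAP's scope, and a later plan may define them. That is possible. Until it does, the protocol's rule is the only one stated.

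**Data are summarized by drug received.** Protocol 8.6 says so, and crossover data might therefore be reported under the long-acting regimen. SAP 3.2 points the other way for its own tables: actual treatment differs from randomized treatment only if it differs for the entire duration. The protocol sentence also does not alter the 30-day window. At best this is ambiguity.

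**Early events dominate.** Injection site reactions were the most common TEAEs in the Phase 1b study, and infusion reactions are monitored during and just after infusion. AEs leading to discontinuation count, and all collected data are listed. All of this stands and limits the loss.

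**Some labs do fall inside.** A reader might infer that no scheduled lab after a second or later dose can count. That is not so: Weeks 78 and 104 have dosing-day draws, and an early discontinuation visit, or a post-study-drug Day 30 visit soon after it, can fall within 30 days of the last dose.

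**Conclusion.** The defect is real and worth correcting. As written, the protocol counts the same long-acting drugs under two windows, and the Group 3 window omits 92% of the required follow-up time after the last dose, or 84% of the last dosing interval. For AEs this is an undeclared protocol–SAP contradiction. For extension labs it is the only rule in the documents.

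A reader might infer that most harms after a crossover participant's last dose go uncounted. The documents do not support that: 92% and 84% are shares of days, and the share of events could be anywhere from about 5% to 92% under the timing assumptions shown. Nor do they support saying that safety is understated in a third of recipients. Group 3 has 25 planned participants, but the extension is optional and conditional, the number crossing over is not given, and only the period after the last dose is affected. If last dose date is set only for participants who have stopped or completed study drug, as SAP 3.8.1 does, the effect at Week 104 is confined mainly to those who have stopped; by the final analysis it reaches every crossover participant.

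**What to change.** 1. In Protocol 8.6, 8.6.2 and 8.6.3, limit the 30-day rule to Group 3's baseline oral ART in the randomized phase, that is, to participants who do not receive the long-acting regimen.
2. From the first long-acting dose, apply the Group 1 rule (no upper limit) to crossover participants for both AEs and labs. Use the last value before that dose as the lab baseline for that period.
3. Record the change in SAP 7.7 and carry the same definitions into the plan for the Week 104 and final analyses.

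The cost is wording only, with no new visits or samples. Group 3 extension AE and lab counts may rise slightly.
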